#### 9. Study Discontinuation

Criteria for discontinuing the study intervention (e.g., halting rules), may include any monitoring test(s) and associated clinical decision point(s) which in the opinion of the clinical investigator, qualified designee, or Data Safety Monitoring Board are viewed as placing the patient at significant risk if Trikafta™ administration is to continue. This could include, for example (but is not limited to) worsening liver function or abnormalities associated with Trikafta™ administration. Discontinuation from Trikafta™ does not mean discontinuation from the study, and remaining study procedures should be completed as indicated by the study protocol. If a clinically significant finding is identified (including, but not limited to changes from baseline) after enrollment, the investigator or qualified designee, and/or Data Monitoring Committee (DMC) (also referred to as Data Safety Monitoring Board, DSMB) will determine if any change in participant management is needed. Any new clinically relevant finding will be reported as an adverse event (AE).

The data to be collected at the time of study intervention discontinuation will include:

- All measurements described for the day 56 follow-up/washout visit

Participants are free to withdraw from participation in the study at any time upon request.

An investigator may discontinue or withdraw a participant from the study for the following reasons:

- If any clinical adverse event, laboratory abnormality, or other medical condition or situation occurs such that continued participation in the study would not be in the best interest of the participant
- Disease progression which requires discontinuation of the study intervention
- If the participant meets an exclusion criterion (either newly developed or not previously recognized) that precludes further study participation
- Participant is unable to receive Trikafta™ for 3 days.
- Pregnancy
- Significant study intervention non-compliance

The reason for participant discontinuation or withdrawal from the study will be recorded. An attempt will be made to replace subjects who sign the informed consent form and receive Trikafta™, and subsequently withdraw, or are withdrawn or discontinued from the study.

A participant will be considered lost to follow-up if he or she fails to return for any scheduled visit and is unable to be contacted by the study site staff.

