## 10. Data Safety Monitoring Plan

Oversight for this trial will be performed by a DSM Chair. A Data Safety Monitoring Board (DSMB) will be selected in consultation with the Chair to specifically oversee the clinical study. The DSMB will consist of at least two physicians experienced in treating patients with cystic fibrosis, a DSMB coordinator and a biostatistician. The DSMB Chair will convene a protocol conference call with committee members so that the DSMB can approve the monitoring plan and review any concerns regarding the current protocol prior to initiation of study enrollment.

The DSMB is primarily responsible for reviewing safety data which will be provided on a continual basis throughout the performance of the study as well as reviewing interim analyses report after four patients have completed the 28-day study drug administration, and again following 50% enrollment (completion of 11 subjects in Substudy 1 and 10 subjects in Substudy 2). The DSMB may recommend early termination or modification of either trial substudy for reasons of study subject safety. Subjects will be monitored for adverse events (AEs) and serious adverse experiences (SAEs) by the Investigators, the study sites' Institutional Review Boards, and the DSMB. The DSMB will also provide recommendations needed to assist the investigative team.

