#### 11. Statistical Methods For a proposed open-label prospective 4-week trial of Trikafta™.

**Substudy 1:** Patients with CF or CFTR-dependent illness who do not have access to modulator therapy but exhibit a clinical phenotype suggestive of partial/residual CFTR activity.

We will serially evaluate clinical outcomes of interest prior to and after the start of therapy. Change in clinical measurements (spirometry, weight/BMI, quality of life, sweat chloride) will be monitored. Our main goals are to determine the clinical response to Trikafta™ and to determine if *in vitro* responsiveness of iPS cells predicts clinical response. The primary outcome is response to Trikafta™ after 4 weeks of treatment. In this study a clinical response to Trikafta™ at week 4 of treatment will be defined as an improvement, from baseline, in  $FEV_1 > 5\%$  predicted and each subject will be classified a responder or non-responder. In this study, if at least 40% of subjects meet the definition of responder, the drug will be considered efficacious (i.e., comparable to the benefit which led to Orkambi™ approval by FDA following trials in F508del homozygotes). Overall response rate will be accompanied by an approximate binomial 95% confidence interval. To determine the role of iPS *in-vitro* response to Trikafta™, we will compare the  $\Delta Isc$  (change in  $Isc$ ) among Trikafta™ responders and Trikafta™ non-responders using a two-sample t-test or a Wilcoxon rank sum test if distributions are skewed. Additionally, we will correlate the  $\Delta Isc$  obtained from *in vitro* experiments with the change in  $FEV_1\%$  predicted (post minus pre) using Spearman's rank-order correlation with an associated 95% confidence interval. We will also test whether the iPS response reaches a CFTR functional threshold of 40% wild-type levels (a magnitude of activity in primary airway epithelial cells viewed as potentially relevant to clinical benefit). In a sensitivity analysis, we will replicate the  $FEV_1$  analysis with sweat chloride responses, and determine the *in vivo* response rate.

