All analyses will be conducted using the intention to treat principal, where all subjects will be included in analysis regardless of how long they took the study medication. Statistical significance will be assessed at the 0.05 level and analyses conducted using SAS v. 9.4 (SAS Institute; Cary, NC).

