#### Sample size

The FDA has suggested that scientifically meaningful 'binning' of patients based on clinical characteristics can help guide future approval of specific patient groups for drug treatment. The present study is not intended for FDA submission or label expansion of Trikafta™, but as a means to determine whether iPS cells differentiated to respiratory phenotype can be used to predict clinical response to CFTR modulators. For the purposes of this protocol, the subjects enrolled, although potentially of different genotypes, will represent a scientifically meaningful cohort or 'bin' of individuals with partial function mutations, sweat chloride < 80 mmol/L, and/or pancreatic sufficiency. This protocol is designed to compare *in vitro* responsiveness of differentiated iPS cells to *in vivo* clinical activity of Trikafta™, and will test the null hypothesis that the true Trikafta™ response rate of CFTR individuals with partial function mutation genotypes is  $\leq 10\%$  vs. the alternative hypothesis that the true Trikafta™ response rate is  $\geq 40\%$ . We will initially enroll four subjects, and expect all of these individuals will show a clinical response (e.g.,  $> 5\%$  improvement of % predicted FEV1 from baseline). If none of the first four subjects exhibit a response, the study will be terminated. Otherwise, we intend to enroll a total sample size of 22 individuals. Subjects who do not complete the study will be replaced. In this design, if Trikafta™ is ineffective, the probability of early termination after four subjects is 66% and only a 5% chance of concluding the drug is effective (type I error). If Trikafta™ is effective, there is an 86.4% chance of reaching this conclusion. If fewer than four patients show a clinical effect, Trikafta™ will be considered ineffective. To demonstrate the ability of iPS cells to predict clinical benefit, 22 patients will provide at least 80% power to detect a significant correlation of at least  $r = 0.55$  between the changes in clinical outcomes with changes in short circuit current as measured in iPS cells. Tabular details of this analysis are provided below. Power calculations were performed using PASS v. 14 (Kaysville, UT) with a two-sided Z-test and a significance level of 0.05.

	Cumulative # of responses	Decision	95% Confidence Interval (CI)

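### Substudy 1 replaces dosed non-completers but promises an analysis of all subjects, and states two different cuts; the 5% type I error fits only 4 and 22 counted subjects and a cut of five

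*Combined protocol and SAP*

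**What the plan says.** All references are to the combined protocol and SAP.

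- **Outcome (section 11, Substudy 1).** Response at week 4 is an FEV1 gain of more than 5% predicted, and "each subject will be classified a responder or non-responder".
- **Analysis set (section 11).** Analyses follow intention to treat, "where all subjects will be included in analysis regardless of how long they took the study medication".
- **Replacement.** Sample size: "Subjects who do not complete the study will be replaced". Section 9 makes clear that dosed subjects are meant: "An attempt will be made to replace subjects who sign the informed consent form and receive Trikafta™, and subsequently withdraw".
- **Design (Sample size).** The null rate is 10% or less and the alternative 40% or more. "If none of the first four subjects exhibit a response, the study will be terminated"; otherwise enrolment continues to 22. The stated figures are 66% early termination and 5% type I error if the drug is ineffective, and 86.4% power.
- **Cut.** Sample size: "If fewer than four patients show a clinical effect, Trikafta™ will be considered ineffective". The decision table instead places four responses on the ineffective side and needs five for its intermediate, possibly-effective verdict. That verdict also carries a condition that the 95% confidence interval contain 40% and have a lower bound above 10%. The top verdict needs 14.
- **Discontinuation (section 9).** Stopping drug does not end study participation. The data collected at that time are "All measurements described for the day 56 follow-up/washout visit", which include spirometry.

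**The concern.** Once one dosed subject is replaced, at least 23 people have been dosed, but the decision counts exist only for 4 and for 4 + 18 = 22. Nothing says whether the leaver, the replacement or both are counted, or what cut applies above 22. Study completion runs to day 56, so a subject with a valid day-28 FEV1 who misses day 56 is a non-completer and would be replaced although already classifiable. A subject with no week-4 FEV1 must still be called a responder or non-responder, without a rule.

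The verdict rests on a small count in an open-label trial. An unstated choice about one or two people could therefore be made with results in view, and could move the Stage 1 stop or the five-response verdict. The disagreement between four and five responses changes the error rate even if nobody leaves.

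**Working it through.** **Inputs.** From Sample size and the decision table: n1 = 4, stop at 0 responses; N = 22; cut c = 5; p0 = 10%; p1 = 40%. The documents give no drop-out rate, so every drop-out figure d below is an assumption.

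**Formula.** P(success) = Σ over x = 1..4 of Bin(4,p)(x) × P[Bin(N−4,p) ≥ c−x].

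**1. The plan's own figures (N=22, c=5).**
- Early termination at 10%: 0.9^4 = 0.656 (stated 66%).
- Type I error: 0.2916×0.0982 + 0.0486×0.2662 + 0.0036×0.5497 + 0.0001×0.8499 = 0.0286 + 0.0129 + 0.0020 + 0.0001 = 0.0436, within the stated 5%.
- Power at 40%: 0.3343 + 0.3428 + 0.1534 + 0.0256 = 0.856 (stated 86.4%, close).

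**2. The other cut.** With c=4 at N=22 the error is 10.75%. Only c=5 is consistent with 5%.

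**3. Leavers kept, count of five alone decides, Stage 1 still four subjects.** Error at a true 10% rate:

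| Chance that a leaver counts as responder | N=23 | N=24 | N=26 |
|---|---|---|---|
| 10%, like the others | 5.0% | 5.7% | 7.1% |
| 5% | 4.7% | 5.0% | 5.7% |
| 0% (other 22 at 10%) | 4.4% | 4.4% | 4.4% |

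**4. Leavers kept, interval condition also applied.** The Wilson lower bound is [p̂ + z²/2n − z√(p̂(1−p̂)/n + z²/4n²)] / (1 + z²/n). At 5/22 this is (0.2273 + 0.0873 − 0.1957)/1.1746 = 10.1%, so it passes. At the same 5/22 the lower bounds are 7.8% (Clopper-Pearson), 5.2% (Wald) and 9.7% (Agresti-Coull), so those three fail. At 5/23 Wilson gives 9.7%. For every N from 23 to 30, five responses fail under all four methods. The Wilson cut becomes 6 for N = 23 to 28, where the error is 1.7% to 3.7%.

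**5. Leavers dropped and replaced, all of them non-responders, all-dosed rate 10%.** The completers' rate is 0.10/(1−d). For d = 5, 10, 15 and 20% the error is 5.2, 6.3, 7.7 and 9.3%. The implied leavers per 22 completers, 22/(1−d) − 22, are 1.2, 2.4, 3.9 and 5.5.

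**6. Stage 1.** At a 40% rate the chance of stopping is 0.6^4 = 13.0%. If one of the first four leaves and is counted as a non-responder, it is 0.6^3 = 21.6%. If that subject is replaced, it returns to 13.0%.

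**The case against.** Several points on the other side are sound.

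- **The interval condition.** A fixed cut of five above 22 ignores the table's requirement on the lower bound, which tightens as N grows. This stands: the 5.0–7.1% arises only if the count alone decides. But the interval method is not named, and three of the four checked contradict the table at 5/22, so the condition cannot be relied on as written.
- **The largest figures need leavers to be dropped.** The 5.2–9.3% contradicts the promise to analyse everyone. It also rests on assumed drop-out and on placing the 10% null on all dosed subjects rather than on completers; with 10% among the 22 completers the error stays 4.36%. Nothing in the documents supports 15–20% drop-out over four weeks. This stands too.
- **Drug-stoppers are largely covered.** They remain in the study and can be classed at day 28. The gap concerns those who leave and those with no week-4 value. Nothing in the documents suggests that discontinuation spirometry stands in for week 4.
- **The discrepancy in the cut is a separate defect.** True, and its effect is larger than that of a few replacements. It belongs here because the same 5% depends on it.

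A reader might infer that replacement inflates the error to 7–9%. The documents do not support that as an expectation, for the reasons above. A reader might also see a conflict in section 10, where the DSMB receives an "interim analyses report after four patients have completed the 28-day study drug administration". That is the trigger for a DSMB report, in a section that ties DSMB termination to safety. Week-4 response cannot be known before week 4, so it is compatible with the futility rule for the first four.

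**Conclusion.** The contradiction is real and its effect is modest. The plan does not define the 4 and the 22 once someone is replaced, gives no rule for a missing week-4 FEV1, and states two cuts. The clearest numerical fault is the cut: 10.75% error under the Sample size sentence against 4.36% under the table, with no leavers at all. For replacement, the 5% is not assured rather than shown to be broken. It reaches 5.0% with one kept leaver who responds like others and 7.1% with four if the count alone decides, but falls below 5% if a Wilson bound is enforced. If leavers are dropped, the 5% describes a completers' rate. The Stage 1 decision is the most sensitive to a single person (13.0% against 21.6%).

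The top verdict (14 or more) and the rule that at least 40% respond (9 of 22) are not materially affected: at a 10% rate their errors are below 0.0001% and about 0.013%. The correlation with iPS cell response, which the plan presents as the study's main purpose, does not depend on these counts.

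**What to change.** 1. Correct the ineffective cut in the Sample size text so that it agrees with the table's cut of five.
2. For the response rate and both stages, count the first 4 and the first 22 dosed subjects in order of enrolment. Use the day-28 FEV1 whenever it was obtained, including after drug was stopped or before a missed day 56. Class subjects without one as non-responders, and do not substitute the discontinuation spirometry.
3. Use replacements only for the iPS correlation and for a completers' sensitivity analysis labelled as such.
4. State that the response count decides, and name the interval method so that the interval column agrees with it; Wilson reproduces the 5/22 row. The Stage 1 entry needs separate correction: it asks for an upper bound below 40%, but at 1 of 4 the Wilson upper bound is 69.9%.
5. Leave the DSMB report trigger in section 10 as it is.

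**Cost.** A few sentences and no change to the 22 planned. Error stays 4.36% for an all-dosed rate of 10%. If completers respond at 40%, the all-dosed rate is 0.40(1−d). At an assumed 5, 10, 15 and 20% missing:

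- Power is 83.1, 80.1, 76.5 and 72.4%, against 85.6%.
- False early stopping, (1−p)^4 with p this all-dosed rate, is 14.8, 16.8, 19.0 and 21.4%, against 13.0%.

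The plan should state both.

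**Alternative.** Keep replacements in the test: count all dosed subjects, with a cut of six fixed in advance for N = 23 to 30. Error is 1.7–4.7%. Power is 83.8–86.8% if leavers respond like others and 82.5% if all are non-responders. The count must again be stated to govern, because the Wilson condition matches a cut of six only up to N = 28.

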#### Sample size

The FDA has suggested that scientifically meaningful 'binning' of patients based on clinical characteristics can help guide future approval of specific patient groups for drug treatment. The present study is not intended for FDA submission or label expansion of Trikafta™, but as a means to determine whether iPS cells differentiated to respiratory phenotype can be used to predict clinical response to CFTR modulators. For the purposes of this protocol, the subjects enrolled, although potentially of different genotypes, will represent a scientifically meaningful cohort or 'bin' of individuals with partial function mutations, sweat chloride < 80 mmol/L, and/or pancreatic sufficiency. This protocol is designed to compare *in vitro* responsiveness of differentiated iPS cells to *in vivo* clinical activity of Trikafta™, and will test the null hypothesis that the true Trikafta™ response rate of CFTR individuals with partial function mutation genotypes is  $\leq 10\%$  vs. the alternative hypothesis that the true Trikafta™ response rate is  $\geq 40\%$ . We will initially enroll four subjects, and expect all of these individuals will show a clinical response (e.g.,  $> 5\%$  improvement of % predicted FEV1 from baseline). If none of the first four subjects exhibit a response, the study will be terminated. Otherwise, we intend to enroll a total sample size of 22 individuals. Subjects who do not complete the study will be replaced. In this design, if Trikafta™ is ineffective, the probability of early termination after four subjects is 66% and only a 5% chance of concluding the drug is effective (type I error). If Trikafta™ is effective, there is an 86.4% chance of reaching this conclusion. If fewer than four patients show a clinical effect, Trikafta™ will be considered ineffective. To demonstrate the ability of iPS cells to predict clinical benefit, 22 patients will provide at least 80% power to detect a significant correlation of at least  $r = 0.55$  between the changes in clinical outcomes with changes in short circuit current as measured in iPS cells. Tabular details of this analysis are provided below. Power calculations were performed using PASS v. 14 (Kaysville, UT) with a two-sided Z-test and a significance level of 0.05.

	Cumulative # of responses	Decision	95% Confidence Interval (CI)
Stage 1: Enter 4 subjects	0	Terminate the trial because the agent is ineffective. Response rate is <math>\leq 10\%</math>	LB of 95% CI is $< 10\%$
	At least 1	Inconclusive result, continue trial (proceed to stage 2).	95% CI contains 10% and the UB is $< 40\%$

Stage 2: Enter 18 additional subjects	4 or less (stage I + stage II)	Consider that the agent is ineffective. Response rate is $\leq 10\%$	LB of 95% CI is less than 10%
	5 or more (stage I + stage II)	Drug may be effective Response rate is greater than 10% and not different from 40%	95% CI contains 40% and LB is $> 10\%$
	14 or more (stage I + stage II)	Drug is effective Response rate is at least 40%	95% CI LB $\geq 40\%$

LB = Lower Bound, UB = Upper Bound

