### **Facilitating modulator availability**

A series of innovative strategies have been devised by pharmaceutical and/or academic groups to address the issue of inadequate CF drug access. In part because a dramatic clinical benefit from modulator treatment can often be obtained within a matter of weeks, N-of-1 trials have been evaluated for a possible role during FDA registration (McGarry et al., 2017; Nick et al., 2014). Such studies are designed so that individual patients serve as their own controls, and a robust drug response can provide data relevant to label expansion. Variability among CF patients with the same genotype, inconsistent clinical findings from a single study subject, preexisting (irreversible) lung injury, disease trajectory (including presence of respiratory exacerbation), and practical barriers to drug approval on a case-by-case basis have limited usefulness of this approach. As an alternative strategy, patients with similar molecular phenotype (e.g., residual CFTR function as judged by *in vitro* testing), and/or evidence of mild clinical disease (pancreatic sufficiency or intermediate sweat chloride values) have been evaluated as a group (independent of underlying gene defect or mechanistic subcategory) (Herper, 2017). In a cohort of patients with rare variants that can be meaningfully binned or designated based on strong scientific rationale, a robust clinical response to CFTR modulators can help promote label expansion to an entire

group of patients with the disease – despite differences in CF genotype for the cohort. While admittedly less ‘precise,’ the situation can be viewed as similar to conventional pharmacotherapies—where registration is based on compelling clinical evidence of benefit to the overall group or enriched study population (for further background, see Schuck et al., 2018).

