### Substudy 2: Patients with N1303K CFTR.

The primary analysis will be to estimate the mean absolute change in sweat chloride concentration from baseline through day 28 among the adolescents and adults with at least one copy of an N1303K mutation and a minimal function mutation who are not currently modulator eligible. A one-sided 0.025 alpha level single sample t-test comparing this estimate to no change will be reported, along with corresponding confidence intervals. A complementary analysis evaluating the percentage of participants with  $\geq 15$  mmol/L decline will also be reported. With a previously estimated 9.7 mmol/L standard deviation of the change in sweat chloride for successful modulator trials previously (Boyle et al., 2014; Vermeulen et al., 2017), an anticipated 6% of responders would be expected by chance alone. Therefore, the treatment response prevalence will be compared to a reference rate of 6%. For longitudinal sweat chloride through day 28 and for secondary endpoints (absolute change in ppFEV1, CFQ-R respiratory domain, and weight/BMI from baseline through day 28), means at each time point and changes over time will be summarized along with corresponding confidence intervals estimated by mixed effects models to account for within-subject correlation.

Changes in sweat chloride following treatment with ETI will be correlated with iPS cell responses in vitro, in addition to secondary clinical outcomes measures. A non-linear Spearman's correlation coefficient will be estimated for each measure paired with iPS cell responses in vitro, with corresponding fitted curves displayed graphically along with coordinates for participant's paired in vivo and in vitro responses. We expect variation both in sweat chloride and in iPS cell short circuit current measurements ( $I_{sc}$ ) due to heterogeneity in genotypic profiles among participants in the study. Sample selection for iPS cell experiments will be coordinated across studies to optimize power and unbiasedness as specified in a sample selection plan.

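### Substudy 1's 10% null is not shown to be the no-effect rate of its own responder criterion, so the stated 66% early stopping and 5% type I error are not established for an ineffective drug

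*Combined protocol and SAP*

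**What the plan says.** In the combined protocol and SAP, Section 11 (Substudy 1) defines response at week 4 as a rise from baseline of more than 5 in FEV1 % predicted, and "each subject will be classified a responder or non-responder". The study is open label, and the same section acknowledges that there is no independent control group.

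The Sample size subsection tests a true response rate of at most 10% against at least 40%, in two stages of 4 and 18 subjects. On the first stage: "If none of the first four subjects exhibit a response, the study will be terminated". It then describes an ineffective drug as having a 66% chance of early termination and "only a 5% chance of concluding the drug is effective (type I error"), and an effective one as having 86.4% power. In the decision table, 5 or more responders out of 22 leads to "Response rate is greater than 10% and not different from 40"%, that is, the drug may work; 14 or more leads to the firm conclusion. The methods text uses another standard: "if at least 40% of subjects meet the definition of responder, the drug will be considered efficacious".

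No source is given for 10%, and no SD of change in FEV1 % predicted appears anywhere. Substudy 2 does take that step for sweat chloride: from a 15 mmol/L cut-off and a previously estimated SD of 9.7 mmol/L, "an anticipated 6% of responders would be expected by chance alone", and 6% becomes its reference rate.

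**The concern.** In a single arm, a subject can cross a fixed threshold because of the drug, because of ordinary variation between two spirometry sessions, or because of a change unrelated to the drug. The no-effect response rate is therefore a property of the threshold and of the spread of change. It cannot simply be chosen. The plan sets it at 10% and then treats a true rate of 10% or less as the same thing as an ineffective drug. The two coincide only if chance alone produces about 10% responders or fewer.

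The background section is aware of the difficulty. Among the limits of using patients as their own controls it lists "inconsistent clinical findings from a single study subject, preexisting (irreversible) lung injury, disease trajectory". That remark concerns N-of-1 trials for registration, but the source of variation is the same.

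Three things depend on the answer: how often the first stage stops a drug that does nothing, how often such a drug reaches the 5-of-22 conclusion, and how many chance responders enter the responder versus non-responder comparison of iPS-cell current, which serves the study's main aim.

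**Working it through.** **Inputs from the documents.** Null 10%; alternative 40%; 4 then 18 subjects; stop on 0 of 4; positive at 5 or more of 22; cut-off 5 points. Substudy 2: cut-off 15, SD 9.7.

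**Assumptions.** Day 28 change is normal with mean 0 when the drug does nothing; points are absolute; the SD of change is unknown, so a range is shown.

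**1. The plan's own figures.** Early termination at 10%: 0.9^4 = 0.656 (stated 66%). The chance of a positive result is the sum, over x = 1 to 4 first-stage responders, of P(x of 4) × P(at least 5 − x of 18).

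- At 10%: 0.2916 × 0.0982 + 0.0486 × 0.2662 + 0.0036 × 0.5497 + 0.0001 × 0.8499 = 0.0436 (stated 5%, so 5% acts as a ceiling).
- At 40%: 0.3456 × 0.9672 + 0.3456 × 0.9918 + 0.1536 × 0.9987 + 0.0256 × 0.9999 = 0.856 (stated 86.4%).

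The design is sound for the null as written. Of the decision rules in the documents, only 5 or more fits the stated error and power together; 4 or more would give 10.8% error at a 10% rate.

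**2. Substudy 2's chance rate.** P(Z > 15/9.7) = P(Z > 1.546) = 6.1%, which reproduces the stated 6%.

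**3. The same step for Substudy 1.** Chance rate = P(Z > 5/SD). It equals 10% when SD = 5/1.2816 = 3.90. The 5-of-22 rule reaches exactly 5% error at a chance rate of 10.4%, which is SD 3.97.

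**4. Error when the drug does nothing, over assumed SDs.**

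| SD of change (points) | Chance responders | Stops at stage 1 | 5 or more of 22 | 9 or more | 14 or more |
|---|---|---|---|---|---|
| 3.0 | 4.8% | 82% | 0.2% | <0.1% | <0.1% |
| 3.5 | 7.7% | 73% | 1.6% | <0.1% | <0.1% |
| 3.9 | 10.0% | 66% | 4.4% | <0.1% | <0.1% |
| 4.0 | 10.6% | 64% | 5.3% | <0.1% | <0.1% |
| 5.0 | 15.9% | 50% | 19% | 0.4% | <0.1% |
| 6.0 | 20.2% | 40% | 35% | 2.0% | <0.1% |
| 7.0 | 23.8% | 34% | 48% | 5.2% | <0.1% |

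Nine of 22 is the smallest count that meets the 40% standard (0.40 × 22 = 8.8).

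**5. Sensitivity to the assumptions.** At SD 3.9, a mean drift of +1 point unrelated to the drug gives P(Z > 4/3.9) = 15.3% chance responders and 17% error; a drift of −1 gives 6.2% and 0.7%. The Sample size subsection words the criterion as an "improvement of % predicted FEV 1 from baseline" of more than 5%. If that means a relative gain, an assumed baseline of 70 makes the cut-off 3.5 points, and the 10% chance rate falls at SD 3.5/1.2816 = 2.73.

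**The case against.** The null is stated openly as a response rate, and the operating characteristics are right for it. Without an SD, the documents cannot show that 10% is too low: at SD 3.5 it is conservative. The plan also limits noise. It requires spirometry meeting ATS acceptability and repeatability criteria, four weeks of clinical stability and, from Day 1, pre-bronchodilator testing where the patient can withhold. The Spearman correlation uses continuous FEV1 change and needs no responder null. The conclusion at 5 or more is hedged, and the plan disclaims FDA submission and label expansion.

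All of this stands, and it sets the limits of the point. A reader might infer that the type I error is shown to be inflated. It is not: the error is unknown, and it could lie on either side of 5%. A reader might also infer that a drug with no effect would readily be declared effective under any of the rules. That does not follow either: at 14 or more the error is negligible, and at 9 or more it reaches 5% only near SD 7.

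What the objection does not supply is a reason for 10%. The rule that is exposed is also the one that the quoted 5% and 86.4% describe. The noise controls may reduce the SD, but the plan never says to what value.

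**Conclusion.** The point holds as a gap in justification. The 66% and 5% are correct for a true response rate of 10%; the plan attributes them to an ineffective drug without showing that the two are the same. Under normal, zero-mean change in absolute points, they are the same only if the SD of Day 28 change is about 3.9 to 4.0 points or less. Beyond that the error of the 5-of-22 rule climbs quickly: one further point of SD, from 4 to 5, takes it from 5.3% to 19%. No SD in the documents says where the trial lies on that curve, so these are conditional figures and not a finding about this trial's actual error rate.

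Should-fix. The repair is mainly wording, and it keeps a count that noise could produce from being read as drug effect.

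**What to change.** 1. **Restate the Sample size claim.** Say that 66% and 5% apply to a true response rate of 10%, and that this means no drug effect only if the SD of change is about 3.9 to 4.0 points or less. Derive the chance responder rate from a prior estimate or from off-treatment data, for example Screening to Day 1 in subjects whose bronchodilator state matches, and show the error over a range of SDs. Do not use the on-treatment SD, because it includes real differences in response. As an illustration, take noise SD 3.5 with 40% of subjects gaining 10 points: the observed SD is √(3.5² + 0.4 × 0.6 × 10²) = 6.0, which implies 20% chance responders when the true figure is 7.7%. Cost: wording and one table.

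2. **Report the mean absolute change in FEV1 % predicted at Day 28 with its confidence interval beside the responder count.** The Substudy 1 methods plan no such estimate. State in advance that 5 or more responders will not be read as evidence of drug effect when the interval includes 0. The data are already collected.

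The second step limits error from noise only. In simulation, the count plus a one-sided 95% lower bound above 0 (the lower limit of a two-sided 90% interval) gave error of 1.3% at SD 4, rising to about 4.4% at SD 8, with zero drift. A +1 point drift unrelated to the drug raised it to about 11% to 15%. If the step becomes a formal success criterion, state the power cost: at a 40% response rate, power is about 85.5%, 83%, 74%, 61% and 48% at SD 4, 5, 6, 7 and 8, against 85.6% for the count alone. A two-sided 95% interval costs more (about 66% at SD 6 and 49% at SD 7). That is a trade-off for the sponsor, and reporting alone avoids it.

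Separately, the decision rules conflict and must be reconciled: fewer than 4 is ineffective in the text, 4 or fewer in the table, 5 and 14 are the table's positive thresholds, and the methods use 40%. Any error rate quoted has to name the rule it belongs to.
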